7.3.1 DSMC SAE Reporting Requirements

The Data Safety Monitoring Committee (DSMC) is responsible for reviewing SAEs for CCCWFU Institutional studies as outlined in Appendix D. All Adverse Events that occur during protocol intervention (defined below) and are coded as either 1) unexpected grade 4, 2) unplanned inpatient hospitalization > 24 hours (regardless of grade), or grade 5 (death) must be reported to the DSMC using the SAE console in WISER.

All CCCWFU Clinical Research Management (CRM) staff members assisting a Principal Investigator in

Cancer within a Pandemic: A Telemental Health Intervention Designed to Augment Psychological Resilience amidst Dual Health Threats

Wake Forest Baptist Comprehensive Cancer Center
WFBCCC #01520

investigating, documenting and reporting an SAE qualifying for DSMC reporting are responsible for informing a clinical member of the DSMC as well as the entire committee via the email notification procedure of the occurrence of an SAE.

8.0 Data Management

Informed consent document	EPIC
Protocol registration form	WISER/OnCore
Coronavirus Anxiety Scale (CAS)	REDCap
Acceptance and Action Questionnaire (AAQ) [free, if a member of ACBS:	REDCap
The Cancer Behaviour Inventory-brief version (CBI-B)	REDCap
The Mini-Mental Adjustment to Cancer (MINI-MAC) 29-item questionnaire	REDCap
UCLA Loneliness Scale Version 3	REDCap
The Impact of Event Scale - Revised (IES-R)	REDCap
Purpose in Life Test	REDCap
Pre-screening questionnaire	REDCap
Group Evaluation Questionnaire	REDCap
Off study/Off Treatment/Survival	WISER/OnCore

This project will utilize REDCap Clinical Data Interoperability Services. This is a special feature for importing data into REDCap from WakeOne. It provides an adjudication process whereby REDCap users can approve all incoming data from WakeOne before it is officially saved in their REDCap project. REDCap Clinical Data Interoperability Services can only be enabled by a REDCap administrator who serves as an honest broker to PHI. REDCap's Clinical Data Interoperability Services can only be accessed by users with valid WakeOne credentials. Using the Clinical Data Interoperability Service requires using the Medical Record Number (MRN) as a key to automatically gather demographics and laboratory data and reduces data entry errors.

9.0 Statistical Considerations

9.1 Analysis of Primary Objective

The primary outcome, the improvement of self-efficacy for young adult cancer survivors navigating pandemic conditions, will be assessed by comparing the change in the Cancer Behaviour Inventory-brief version (CBI-B) from baseline to Visit 8. With an n of 15, power of 80% and a 2-sided alpha of 0.05, the confidence interval around our baseline, Visit 4, Visit 8, and change scores would have a width of

Cancer within a Pandemic: A Telemental Health Intervention Designed to Augment Psychological Resilience amidst Dual Health Threats

Wake Forest Baptist Comprehensive Cancer Center
WFBCCC #01520

approximately 1.02 standard deviations. To test the change over the 8 weeks, a paired t-test (using the baseline and Visit 8 scores within the same patient) will be used; the expected difference in the CBI-B between the 2 scores would be no change (null hypothesis is mean is equal to 0). We would also calculate the difference between baseline and Visit 4 and test to see if that mean is significantly different from 0; this will help us understand that if a change occurs, does it occur earlier in the intervention or does the change happen closer to the end of the intervention.

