6.0 Intervention Plan

The study aims to initially recruit a single cohort of 15 patients. This is a virtual group interventional design in which investigators distribute the electronic assessment battery, perform the intervention, assess mid-way through, and reassess post-intervention. The virtual group will be conducted within a secure platform such as Microsoft WebEx. Assessments (pre-, post-, mid-way) will be distributed through REDCap, a secure virtual platform, as will session handouts and forms. If participants do not have headphones, these will be provided by the study team. The biostatistician will assist with the assessment of change over time within the instrumentation. The session content for this group is built on clinical experience and empirically informed practices, drawing upon elements of Acceptance and Commitment Therapy and Meaning Making approaches. Investigators/facilitators believe that in these unique times, it is optimal to pull elements from various (manualized) approaches that contribute important elements to the group experience. In short, we are making intentional decisions within session design in which we draw heavily from empirically supported practices yet combine them in a manner that seems appropriate for the circumstances based on clinical judgment.

The intervention will be conducted by graduate-prepared mental health providers who are licensed or working under the supervision of a licensed provider. Providers will co-facilitate at all times, with two providers available to respond to group dynamics and follow up with individual members as needed.

The clinicians leading the group will adhere to professional, legal, and ethical guidelines of confidentiality established by professional organizations and state law. Legal and ethical exceptions to confidentiality include: A clear or present danger that the patient intends to harm her/himself or another, knowledge of the abuse or neglect of a minor child or incapacitated adult, or responses to a court subpoena or as otherwise required by law. All members of the group will be required to sign confidentiality forms, in which they agree not to disclose

Cancer within a Pandemic: A Telemental Health Intervention Designed to Augment Psychological Resilience amidst Dual Health Threats

Wake Forest Baptist Comprehensive Cancer Center
WFBCCC #01520

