9.2 Analysis of Secondary Objectives

To reduce depression and anxiety levels through meaning-making, three instruments will provide information on baseline, Visit 8, and change over time. The CAS, MINI MAC, and Purpose in Life Test will all be utilized to estimate depression and anxiety levels. With an n of 15, the width of the confidence interval around the baseline, Visit 4, Visit 8, and change between baseline and Visit 4 as well as Visit 8 scores would be approximately 1.02 standard deviations; a paired t-test will be used to assess the change in the scores. As this is a pilot study, no adjustment in the p-value will be done for multiple comparisons.

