9.3.4 To observe improvement in psychological resilience and flexibility skills in participants, the Acceptance and Action questionnaire (AAQ) will be used to estimate flexibility. As in 9.1, with an n of 15, the width of the confidence interval around the baseline, Visit 4, Visit 8, and change between baseline and Visit 4 and baseline and visit 8 scores would be approximately 1.02 standard deviations; a paired t-test will be used to assess the change in AAQ. As this is a pilot study, no adjustment in the p-value will be done for multiple comparisons.

9.3.5 To reduce feelings of helplessness and hopelessness, the MINI MAC will be used. With an n of 15, the width of the confidence interval around the baseline, Visit 4, Visit 8, and change between baseline and Visit 4 as well as Visit 8 scores would be approximately 1.02 standard deviations; a paired t-test will be used to assess the change in the scores. As this is a pilot study, no adjustment in the p-value will be done for multiple comparisons.

9.3.6 To increase distress tolerance, the Impact of Event Scale (IES) will be used to assess this measure. With an n of 15, the width of the confidence interval around the baseline, Visit 4, Visit 8, and change between baseline and Visit 4 as well as Visit scores would be approximately 1.02 standard deviations; a paired t-test will be used to assess the change in the scores. As this is a pilot study, no adjustment in the p-value will be done for multiple comparisons.

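### The Visit 4 test in section 9.1 shows whether CBI-B change is detectable by mid-point, but not whether change came mainly early or late

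*Combined protocol and SAP*

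**What the plan says.** Section 6.0 describes one group of 15 with no control arm, in which investigators "perform the intervention, assess mid-way through, and reassess post-intervention". The activities table in section 6.1 schedules the CBI-B before the study, at the mid-point after week 4, and after the study. I take the last two to be the Visit 4 and Visit 8 scores of section 9.

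The primary analysis in 9.1 is a paired t-test of baseline against Visit 8. Section 9.1 then adds that the team will "calculate the difference between baseline and Visit 4 and test to see if that mean is significantly different from 0". The reason given is that "this will help us understand" the timing: "if a change occurs, does it occur earlier in the intervention or does the change happen closer to the end".

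Intervals are also planned for the scores and change scores. Section 9.3.4 spells out which changes are meant. It opens "As in 9.1, with an n of 15" and lists "change between baseline and Visit 4 and baseline and visit 8 scores would be approximately 1.02 standard deviations". Section 9.2 uses the looser phrase "change between baseline and Visit 4 as well as Visit 8 scores", which I read the same way. Both planned changes therefore start at baseline.

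**The concern.** Early against late is a comparison of two quantities: the change from baseline to Visit 4 and the change from Visit 4 to Visit 8. The Visit 4 test concerns only the first. Its chance of rejecting is the same whatever happens afterwards.

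Setting it beside the Visit 8 test compares two significance results rather than the two halves. A significant Visit 8 result with a non-significant Visit 4 result is not evidence that change was late, because under steady improvement only half the change is present at Visit 4 and power there is lower. A significant Visit 4 result correctly shows some change by mid-point, but not that most of the change was early. Steady improvement has no category of its own.

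What is at stake is a possible unsupported statement, in the pilot report, about when the primary outcome moved.

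**Working it through.** **The plan's own figure.** The stated interval width at n=15 is about 1.02 SD. The normal formula gives 2 × 1.960/√15 = 1.012; the half-width 0.506 rounds to 0.51, and doubling gives 1.02. The t-based width is 2 × 2.145/√15 = 1.108. The point below does not depend on this figure.

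**What can be recovered from the planned estimates.** With complete data, mean(V8 − V4) = mean(V8 − V0) − mean(V4 − V0), so the late mean change follows by subtraction. Its interval does not: Var(V8 − V4) = Var(V8 − V0) + Var(V4 − V0) − 2 Cov(V8 − V0, V4 − V0), and the covariance is not among the planned outputs.

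**Independence from later data.** A change of 0.5 SD by Visit 4 is detected with power 44% (non-central t, 14 df, non-centrality 0.5 × √15), whether the Visit 8 change is 0.5, 1.0 or 1.5 SD.

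**Inputs for the size.**
- From the plan: n = 15 and two-sided alpha 0.05.
- Assumed, because the documents give no effect size, SD or correlation for the CBI-B: complete data, normal scores, and a total change d in SDs of the baseline-to-Visit-8 change. d = 0.778 gives 80% power at Visit 8.
- Assumed reading rule, not in the plan: *late* if only Visit 8 is significant, *early* if both are.
- Assumed structures: A, equal SDs of change (compound symmetry). B, AR(1) with r = 0.5 per half. C, AR(1) with r = 0.73 per half; the value is borrowed from the two-month retest figure that section 6.2 gives for the UCLA scale. D, random slopes with error variance 0.25 of the slope variance (slope over the full period). E, as D with 0.01, an extreme case.

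**SD ratios.** Mid change is V4 − V0, end change is V8 − V0, and the contrast is (V8 − V4) − (V4 − V0) = V8 − 2V4 + V0. Variances of mid, end and contrast:
- A (r = 0.5 and unit variance; the ratios do not depend on r): 1, 1, 3
- B: 2(1 − r) = 1; 2(1 − r²) = 1.5; 6 − 8r + 2r² = 2.5
- C: 0.54; 0.934; 1.226
- D: 0.25 + 0.5 = 0.75; 1 + 0.5 = 1.5; 6 × 0.25 = 1.5
- E: 0.27; 1.02; 0.06

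**Steady change.** Half of d is present at Visit 4, so the standardised mid effect at d = 0.778 is 0.389 divided by the mid/end SD ratio; power comes from the non-central t. The joint behaviour of the two tests comes from 200,000 simulated trials per scenario.

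| Structure | mid/end SD | Visit 4 power, d = 0.778 | Looks late, d = 0.5 | d = 0.778 | d = 1.0 | d = 1.5 |
|---|---|---|---|---|---|---|
| A | 1.000 | 0.290 | 0.758 | 0.661 | 0.545 | 0.229 |
| B | 0.816 | 0.405 | 0.650 | 0.524 | 0.377 | 0.088 |
| C | 0.760 | 0.454 | 0.602 | 0.461 | 0.313 | 0.057 |
| D | 0.707 | 0.510 | 0.543 | 0.391 | 0.245 | 0.032 |
| E | 0.514 | 0.777 | 0.117 | 0.052 | 0.019 | 0.000 |

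The looks-late columns give the share of trials significant at Visit 8 that are not significant at Visit 4.

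**The contrast.** Under steady change its true mean is zero, and it rejects in about 5% of trials in every structure. Its mean 95% half-width is 2.145 × 0.982/√15 = 0.544 times the contrast/end SD ratio, where 0.982 is the expected sample SD as a fraction of the true SD at 14 df. With ratios 1.732, 1.291, 1.146, 1.000 and 0.243, the half-widths are 0.94, 0.70, 0.62, 0.54 and 0.13 SD of the end change.

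**The case against.** The plan does not say that the Visit 4 test decides timing. It says only that the test helps, and it sets that test beside the Visit 8 test and the intervals. A reader might infer that timing will be called from the pair of p-values. The documents state no such rule, so the percentages above describe an assumed reading and are not an error rate of the plan. This stands, and the point is worded accordingly.

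A reader might also count a significant Visit 4 result as an error when most of the change is late. With 30% of the change in the first half it occurs in 16% to 46% of end-significant trials at 0.778 SD. It is a true detection of change by mid-point, and misleads only if reported as mainly early.

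For a pure dichotomy the existing test does well. At 0.778 SD with all change early, Visit 4 misses in only 15%, 3.4%, 1.5%, 0.5% and 0% of end-significant trials (A to E). With all change late it is non-significant in about 96%, although *late* is then also the default label. The contrast has power of only 37%, 58%, 69% and 80% in A to D when all change is in one half. Its advantage is with steady change, where it keeps its 5% error. Nor would steady change be mislabelled late often at large effects: at 1.5 SD the rate is 23% or less.

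**Conclusion.** The point holds as a limited one. The Visit 4 test answers whether change is detectable by mid-point; alone it cannot separate early from late change, and nothing else in sections 9.1 to 9.4 compares the two halves. That much follows from the definitions and needs no assumption.

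The size does rest on assumptions: the reading rule, complete data, the effect size and the correlation structure. On those, steady change with 80% end power would look late in 39% to 66% of end-significant trials in A to D and 5% in E. At 1.5 SD the range in A to D is 3% to 23%.

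A reader might infer that the primary result is compromised. It is not: the baseline-to-Visit-8 paired test does not use Visit 4. Timing is also not among the objectives in 2.1 to 2.3 or the outcomes in 5.1 to 5.3, and this is a 15-person pilot. It is a minor improvement to a supportive analysis.

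**What to change.** In 9.1, for the CBI-B, add two estimates, each with a t-based 95% confidence interval: the change from Visit 4 to Visit 8, and the within-person contrast (Visit 8 minus Visit 4) minus (Visit 4 minus baseline). Base any early or late statement on the contrast, and call timing undetermined if its interval includes zero. Describe the Visit 4 test only as showing whether change is detectable by mid-point. If the contrast is not added, reword the sentence in that way at least.

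The cost is one or two sentences and one extra calculation, from scores already scheduled at all three times. The drawback is imprecision. For a 30/70 early/late split at 1.0 SD, the contrast has power of 13%, 20%, 24% and 30% in structures A to D, and 80% power would need about 150, 84, 67 or 52 subjects. An undetermined result will be common, so the practical gain is mainly an honest interval and more cautious wording.

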9.2 Analysis of Secondary Objectives

To reduce depression and anxiety levels through meaning-making, three instruments will provide information on baseline, Visit 8, and change over time. The CAS, MINI MAC, and Purpose in Life Test will all be utilized to estimate depression and anxiety levels. With an n of 15, the width of the confidence interval around the baseline, Visit 4, Visit 8, and change between baseline and Visit 4 as well as Visit 8 scores would be approximately 1.02 standard deviations; a paired t-test will be used to assess the change in the scores. As this is a pilot study, no adjustment in the p-value will be done for multiple comparisons.

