5.3 Exploratory Analyses

- 5.1.3 To assess the feasibility of conducting a telehealth support group for cancer survivors within a pandemic.
- 5.1.4 To assess YA cancer survivors' interest in participation in a telehealth support group within a pandemic.
- 5.1.5 To enhance participants' strategies for engaging social connectivity and reduce feelings of isolation amidst simultaneous forces promoting self-isolation (i.e., cancer diagnosis and pandemic).
- 5.1.6 To reduce feelings of helplessness.
- 5.1.7 To observe improvement in psychological resilience and flexibility skills in participants.
- 5.1.8 To increase distress tolerance.

Cancer within a Pandemic: A Telemental Health Intervention Designed to Augment Psychological Resilience amidst Dual Health Threats

Wake Forest Baptist Comprehensive Cancer Center
WFBCCC #01520

Table 1: Study Measures		
Type/Purpose of Measure	Variable	Measures
Primary Outcomes	Self-Efficacy	Cancer Behaviour Inventory-brief version (CBI-B)
Secondary Outcomes	Depression and Anxiety Level	CAS, MINI MAC, and Purpose in Life Test
Exploratory Analyses	Feasibility Interest Social Connectivity Psychological resilience and flexibility skills Helplessness and Hopelessness Distress tolerance	Number of subjects participating at the final visit Number of Sessions Attended UCLA Loneliness Scale Acceptance and Action questionnaire (AAQ) MINI MAC Impact of Event Scale (IES)

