6.2 Intervention Administration

Instrumentation

Coronavirus Anxiety Scale (CAS)

“CAS is a reliable instrument ($\alpha > .90$), with solid factorial (single-factor; invariant across sociodemographics) and construct (correlated with anxiety, depression, suicidal ideation, and drug/alcohol coping) validity. The diagnostic properties of the CAS (90% sensitivity and 85% specificity) are comparable to related screening instruments, such as the Generalized Anxiety Disorder-7” (Lee, 2020).

Acceptance and Action Questionnaire (AAQ)

Acceptance and Action questionnaire (AAQ) assesses psychological inflexibility. It has been found to have high internal consistency and reliability across different types of psychopathology illnesses and different target groups.

Cancer Acceptance and Action Questionnaire

This 18-item questionnaire is used to assess psychological flexibility in cancer patients. It presents experiences such as avoidance and painful memories.

The Cancer Behaviour Inventory-brief version (CBI-B)

12-item validated questionnaire used widely as a measure of self-efficacy for coping with cancer, derived from the longer 33-item version. CBI-B has been reported to have good internal reliability ($\alpha = 0.84$) and construct validity. The CBI-B measures coping self-efficacy.

The Mini-Mental Adjustment to Cancer (MINI-MAC) 29-item questionnaire

The Mini-MAC is a 29-item questionnaire measures patients’ present experiences using a 4-point Likert scale ranging from “Definitely does not apply to me” (1) to “Definitely apply to me” (4). Five subscales include: Helpless–Hopeless, Anxious Preoccupation, Cognitive Avoidance, Fighting Spirit and Fatalism.

UCLA Loneliness Scale Version 3

A 20-item scale designed to measure one’s subjective feelings of loneliness as well as feelings of social isolation. Participants rate each item on a scale from 1 (Never) to 4 (Often). The measure has high internal consistency (coefficient alpha = .96) and a test-retest correlation over a two-month period of .73.

The Impact of Event Scale - Revised (IES-R)

Cancer within a Pandemic: A Telemental Health Intervention Designed to Augment Psychological Resilience amidst Dual Health Threats

Wake Forest Baptist Comprehensive Cancer Center
WFBCCC #01520

A short, easily administered self-report questionnaire that has eight intrusion and eight avoidance items, derived from the original IES. Six additional items assess for hyperarousal.

The Purpose in Life Test

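### Section 9.2 and Table 1 use three scales to estimate depression and anxiety, but the section 6.2 descriptions support none of them for depression, and support the Purpose in Life Test for neither construct

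*Combined protocol and SAP*

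**What the plan says.** The secondary objective (2.2.1, repeated under 5.2) is to lower depression and anxiety by way of meaning-making. Table 1 names the outcome "Depression and Anxiety Level" and lists "CAS, MINI MAC, and Purpose in Life Test" against it. Section 9.2 repeats the assignment: "The CAS, MINI MAC, and Purpose in Life Test will all be utilized to estimate depression and anxiety levels". It plans paired t-tests for the changes from baseline to Visit 4 and to Visit 8, with no multiplicity adjustment, and names no Mini-MAC subscale.

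The Mini-MAC also has an exploratory role. Table 1 lists it for "Helplessness and Hopelessness", and section 9.3.5 says: "To reduce feelings of helplessness and hopelessness, the MINI MAC will be used".

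Section 2.0 lists purpose and meaning among the expected improvements. It lists anxiety, depression, and helpless or hopeless feelings as separate items among the expected reductions.

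**The concern.** Section 6.2 is where the protocol says what each instrument measures, and it does not match the use made of these scales in Table 1 and section 9.2. Two things are at stake.

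- **Purpose in Life Test.** A rise in purpose and meaning, which the sessions set out to teach, would be reported as an improvement in depression and anxiety. The pathway named in the objective would be counted as its outcome.
- **Depression.** Section 1.0 names depression as a target, section 2.0 as a hypothesis, and sections 2.2.1 and 5.2 as a secondary objective and outcome. Section 7.3 calls the study a treatment for concerns that include depression. Any conclusion about it would rest on no instrument that section 6.2 describes as measuring it.

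Section 9.3 expects the feasibility and attendance data to help design future studies. If the clinical outcomes are used in the same way, the label on each of them matters.

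**Working it through.** **The plan's own figure.** Section 9.2 gives a confidence interval width of about 1.02 SD at n = 15. The normal approximation gives 2 × 1.960 / √15 = 3.920 / 3.873 = 1.012 SD, within 1% of the stated value. (With the t distribution on 14 degrees of freedom it is 1.108 SD.) The figure is in SD units, so it is the same for any scale and says nothing about which construct a scale measures. The question has to be settled by comparing the text.

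**The three secondary instruments.**

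| Instrument | Use in 9.2 and Table 1 | Description in 6.2 |
|---|---|---|
| CAS | Depression and anxiety | Single-factor coronavirus anxiety scale. Depression appears only in its construct validity: "correlated with anxiety, depression, suicidal ideation, and drug/alcohol coping" |
| Mini-MAC | Depression and anxiety, subscale not stated | Five subscales: Helpless–Hopeless, plus "Anxious Preoccupation, Cognitive Avoidance, Fighting Spirit and Fatalism". One is named for anxiety, none for depression |
| Purpose in Life Test | Depression and anxiety | 20 items on purpose and meaning in life. Neither depression nor anxiety is mentioned |

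A correlate of a scale is not the construct it measures. Otherwise the CAS would equally be a measure of suicidal ideation or of drug and alcohol coping.

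**Does another instrument fill the gap?** The activity schedule marks seven outcome instruments at pre-study, mid-point and post-study. Besides the three above, these are the AAQ (psychological inflexibility), CBI-B (coping self-efficacy), UCLA Loneliness Scale (loneliness and isolation) and IES-R (intrusion, avoidance, hyperarousal). Described as a depression measure: 0 of 7. Section 6.2 also describes the Cancer Acceptance and Action Questionnaire, which is not in the schedule or the section 8.0 list: "This 18-item questionnaire is used to assess psychological flexibility in cancer patients". It would not fill the gap either.

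**Do the documents treat these as one construct?** No. Section 2.0 lists purpose and meaning, depression, and helpless or hopeless feelings as separate items. Table 1 and section 9.3.5 give helplessness and hopelessness their own exploratory analysis.

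**Tests affected.** Section 6.2 gives no subscales for the Purpose in Life Test, so I take it as one score. One score × two changes (baseline to Visit 4, baseline to Visit 8) = 2 paired t-tests reported under a construct that the description does not support.

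**The case against.** The best defence is that the objective works through meaning-making, so the Purpose in Life Test belongs in section 9.2. That stands as a reason to analyse it there as a measure of the pathway. It is not a reason to call it an estimate of depression or anxiety.

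A second defence is that section 6.2 holds only short summaries. Silence there does not show that a scale cannot act as a proxy for depression, and the CAS summary does report a correlation with it. This also stands. A reader might infer that the trial cannot learn anything about depression from these scales. The documents do not establish that; they show only that no description supports the use, and no rationale for a proxy is given.

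A reader might also infer that the Mini-MAC Helpless–Hopeless score will be reported twice, as depression in 9.2 and as helplessness in 9.3.5. That does not follow, because 9.2 names no subscale. What is documented is the unspecified score, and double reporting is only one way it could be resolved.

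Finally, this is a 15-person pilot with no planned composite, so each instrument's result stays identifiable. That limits the consequence but does not remove the mislabelling.

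**Conclusion.** The point holds as a mismatch between section 9.2 and Table 1 on one side and section 6.2 on the other. No instrument is described in section 6.2 as measuring depression (0 of the 7 scheduled outcome instruments). Of the three secondary instruments, the Purpose in Life Test is described as measuring neither construct, and its two paired t-tests would carry the wrong label. Anxiety is covered within limits: the CAS is specific to coronavirus, and the Mini-MAC has one subscale named for anxiety, though 9.2 does not select it.

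The damage is confined to what the secondary objective can conclude. It would be wrong to read this as biased results: no individual score estimate is distorted, and the CBI-B primary analysis is unaffected. The conclusion rests on taking section 6.2 as the protocol's statement of what each instrument measures. It makes no claim about validation work outside the documents.

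**What to change.** (a) In Table 1 and section 9.2, report the Purpose in Life Test as its own outcome, purpose and meaning. It may stay in 9.2 as the measure of the meaning-making pathway, but not as an estimate of depression or anxiety.

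(b) Name the CAS as a coronavirus-specific anxiety outcome. Have the investigators state which Mini-MAC subscale or subscales serve 9.2 and which serve 9.3.5, so that no subscale is reported under two construct labels.

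(c) Then choose one of two routes for depression.

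- **Remove it as a measured outcome** from 2.0, 2.2.1, 5.2, Table 1 and 9.2, and align the wording in 1.0 and 7.3. The price is that the pilot does not report on a construct it says it targets.
- **Measure it.** Add one brief validated self-report depression scale to the three existing REDCap batteries, enter it in Table 1, the activity schedule, 6.2 and 8.0, and analyse it with the same paired t-test. This works only if it is done before the pre-group battery is sent to the single cohort; after that there is no baseline. The cost is at most 15 × 3 = 45 forms, and fewer with any dropout.

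Steps (a), (b) and the removal route are wording changes that need no new data.
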